## 5.3.7. Per-protocol Analysis

The primary analyses for primary endpoint will also be performed on per-protocol analysis set (Section 2.4.1.2). Similar data handling rules specified in Section 5.2.2 will apply.

## 5.4. Secondary Efficacy Variable(s)

In addition to the primary, the analyses for secondary efficacy endpoints will be performed and nominal p-values will be provided. Other efficacy endpoints include the endpoints related to

- HiSCR
- Lesion Count
- Modified Hidradenitis Suppurativa Score (mHSS)
- HS-PGA
- Patient-reported Outcomes
  - Numerical Rating Scale (NRS) for Pain & Itch [take home patient diary]
  - DLQI
  - HSSD
  - HADS
  - Health Status Questionnaire (EQ-5D-3L)
  - Patient's Global Impression of Severity (PGI-s)
  - Patient's Global Impression of Change (PGI-c)
- Exploratory endpoints
  - International Hidradenitis Suppurativa Severity Score System (IHS4)
  - Hidradenitis Suppurativa Quality of Life Measure (HiSQOL)
  - Physician's Global Assessment of Inflammatory Skin Disease (PGA-ISD)

## 5.4.1. Analysis Methods

The secondary efficacy analyses outlined in the following sections in general will be carried out at key endpoints (Week 12 and Week 16) and over time.

Most of the secondary efficacy analyses described in sections below will be based on FAS. For participants randomized to placebo, only participants who crossed over to receive bermekimab at Week 16 will be included in the efficacy summaries for the visits after Week 16. All statistical testing will be performed at the 2-sided 0.05 significance level. Nominal p-values will be presented.

## 5.4.1.1. At Week 12 and Week 16

For continuous endpoints where longitudinal data were collected prior to the analysis visits; treatment comparisons will be performed using Mixed-Effect Model Repeated Measure (MMRM) model, with fixed effects for treatment, week, stratification factors (prior biologic use (yes/no), screening Hurley stage (II/III)) when sample size in each category of the stratification variables is permitted, and baseline value in the model. The MMRM model will also include prior biologic use by visit, screening Hurley stage by visit, and baseline value by visit interaction and the treatment-by-week interaction as additional explanatory factors.

The model will be performed based on all available data from the 3 treatment groups through Week 16. The treatment difference between a guselkumab group and the placebo group will be estimated by the difference in the least squares means (LSmeans). The 95% CIs for the differences in LSmeans and p-values will be calculated.

For binary response endpoints treatment comparisons will be performed using a Cochran-Mantel-Haenszel (CMH) test stratified by the prior biologic use (yes/no) and screening Hurley stage (II/III) with missing data imputed with Non-Responder Imputation (NRI) defined in Section 5.2.2.

For the PRO endpoints with ordinal scale, the Cochran-Mantel-Haenszel (CMH) mean scores test stratified by prior biologic use (yes/no) and screening Hurley stage (II/III) will be used to compare bermekimab and placebo. The distribution of ordinal scale category will also be provided.

## 5.4.1.2. Over Time Summaries

In general, all endpoints with over time analyses will be descriptively summarized by treatment groups using descriptive statistics, such as mean, median, standard deviation, interquartile range, minimum and maximum for continuous variables, and counts and percentages for categorical variables.

For continuous secondary endpoints, the change from baseline at each week will be analyzed using a restricted maximum likelihood (REML)-based mixed model for repeated measures (MMRM) with fixed effects for treatment, visit, stratification factors (prior biologic use (yes/no) and screening Hurley stage (II/III)), baseline value, prior biologic use by visit, screening Hurley stage by visit, baseline value by week interaction, and the treatment-by-week interaction. Least Square means (LSmeans), LS means differences and their corresponding 95% confidence interval will be provided over time through Week 16 by visit and treatment group in addition to the descriptive summary statistics. For over time summaries from Week 16 through Week 36. Least Square means (LSmeans) and their corresponding 95% confidence interval will be provided.

Additionally, graphical data displays may also be used to summarize the over time data if applicable.

#### 5.4.2. Data Handling Rule

Unless otherwise specified, data handling rules specified in Section 5.2.2 will be applied to these secondary analyses. For binary endpoints, participants with missing response status will be considered non-responders for the over time analyses.

#### 5.4.3. Secondary Efficacy Endpoints

#### 5.4.3.1. Hidradenitis Suppurativa Clinical Response (HiSCR)

#### 5.4.3.1.1. Definition

- HiSCR75 is defined as a  $\geq$  75% reduction in inflammatory lesion AN count (sum of abscesses and inflammatory nodules) from baseline and no increase in abscesses or draining fistulas in HS compared with the lesions counted at baseline.
- HiSCR90 is defined as a ≥ 90% reduction in inflammatory lesion AN count (sum of abscesses and inflammatory nodules) from baseline and no increase in abscesses or draining fistulas in HS compared with the lesions counted at baseline.

Please also refer to Section 5.3.1 for the definition of the HiSCR responder status.

#### 5.4.3.1.2. Analysis Related to HiSCR

- The proportion of participants who achieved HiSCR at Week 16 will be compared between each of the bermekimab groups and the placebo group.
- The proportion of participants who achieved HiSCR75 and HiSCR90 at Week 12 and Week 16 will be compared between each of the bermekimab groups and the placebo group.
- The proportion of participants who achieved HiSCR, the proportion of participants who achieved HiSCR by baseline weight category (≤ 95 kg, > 95 kg), and the proportion of participants who achieved HiSCR by baseline Hurley stage (II/III) will be summarized by treatment group over time.
- The proportion of participants who achieved HiSCR75 and HiSCR90 will be summarized by treatment group over time.

Subgroup analyses specified in Section 5.3.6 will also be performed at Week 16. In addition, for participants who discontinued study treatment or have missing data, the proportion of participants who achieve HiSCR through Week 16 will be analyzed utilizing the hypothetical estimand (i.e. MI method) and treatment policy estimand (i.e. observed data).

## 5.4.3.2. Lesion Count

#### 5.4.3.2.1. Definition

Lesion counts are defined as the number of abscesses, inflammatory nodules, non-inflammatory nodules, draining fistulas, and non-draining fistulas. Lesions will be counted during each visit.

- AN count is defined as total abscess and inflammatory nodule count.
- AN50 is defined as at least a 50% reduction in AN count relative to baseline.

- AN75 is defined as at least a 75% reduction in AN count relative to baseline.
- AN90 is defined as at least a 90% reduction in AN count relative to baseline.
- AN100 is defined as a 100% reduction in AN count relative to baseline (ie, AN count = 0).

## 5.4.3.2.2. Analysis Related to Lesion Count

#### AN Count

- The change from baseline in total AN count at Week 12 and Week 16 will be compared between each of the bermekimab groups and the placebo group respectively.
- The change from baseline in total AN count will be summarized by treatment groups over time.
- The proportion of participants achieving at least 50%, 75%, 90%, and 100% reduction in total AN count at Week 12 and Week 16 will be compared between each of the bermekimab groups and the placebo group.
- The proportion of participants achieving at least 50%, 75%, 90%, and 100% reduction in total AN count will be summarized by treatment group over time. In addition, the proportion of participants achieving at least 50%, 75%, 90%, and 100% reduction in total AN count will be summarized in subgroups of baseline weight category ( $\leq$  95 kg, > 95 kg) and baseline Hurley stage (II/III) by treatment group over time.
- The proportion of participants achieving AN count of 0/1 and 0/1/2 respectively at Week 12 and Week 16 will be compared between each of the bermekimab groups and the placebo group.
- The proportion of participants who experienced at least one flare (defined as at least a 25% increase in AN count with a minimum increase of 2 AN count relative to baseline) over 16 weeks will be compared between each of the bermekimab groups and the placebo group at Week 12 and Week 16. Furthermore, the proportion of participants who experience at least one flare over 36 weeks will be summarized at Week 36 by treatment groups.

In addition, two supplementary analyses will be performed for the analyses (a) change from baseline in AN count at Week 12 and week 16 and (b) change from baseline in AN count overtime (Section 5.2.2) by using

- Observed data regardless of whether the subject discontinued treatment or have missing data.
- Data after treatment discontinuation will be considered as missing, missing data will be addressed by MMRM model.

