4. ELIGIBILITY CRITERIA

4.1 INCLUSION CRITERIA

No waivers/exemptions will be granted for protocol inclusion/exclusion criteria.

Subjects are included in the study if they meet all of the following criteria:

- Written informed consent provided by the patient.
- Male or female, age ≥ 18 years.
- Naïve to OR failure of prior targeted biologic therapy for HS (including anti-TNF, anti-IL-17, or JAK inhibitor therapy).
- Must agree to daily use (throughout the entirety of the study) of one of the following over-thecounter treatments to the body areas affected with HS lesions: either soap and water, or a topical antiseptic wash containing chlorhexidine gluconate, triclosan, or benzoyl peroxide, or a dilute bleach bath.
- Diagnosis of HS for at least 1 year prior to screening.
- HS affecting at least two distinct anatomic areas, one of which is Hurley II or III stage.
- A total body count of abscesses and inflammatory nodules (A+N) of at least 3.
- Full understanding of the procedures of the study protocol and willingness to comply with them.

- In case of female patients of childbearing potential, willingness to use one method of contraception of high efficacy during the entire study period. This method can be hormonal contraceptives or one of the following: condoms, diaphragm, or an intrauterine device. Women of non-childbearing potential include those considered to have a medical history that indicates that pregnancy is not a reasonable risk, including post-menopausal women and those with a history of hysterectomy or surgically sterilized.
- Males participating in this clinical research study should not get a sexual partner pregnant during participation in this research study as the effect of the study drug on sperm is not known.

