#### 4.1. Demographics and Baseline Characteristics

The FAS will be used for all tabulations. Participants' demographic data and baseline disease characteristics will be summarized by treatment group. If imbalances are found at baseline, then additional analyses may be performed adjusting for baseline differences.

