## 5. EFFICACY

## 5.1. General Method of Analysis

Unless specified otherwise, efficacy data summaries will be provided by treatment group for the FAS. Statistical comparisons will be made between each of the bermekimab treatment groups (400 mg SC qw, 400 mg SC q2w) and the placebo treatment group.

In general, for response efficacy endpoints, treatment comparisons will be performed using a Cochran-Mantel-Haenszel (CMH) test stratified by the prior biologic use (yes/no) and screening Hurley stage (II/III). For continuous efficacy endpoints, treatment comparisons will be performed using either a Mixed-Effect Model Repeated Measure (MMRM) model. All of the models will have treatment group, prior biologic use (yes/no), screening Hurley stage (II/III), and baseline value for the corresponding efficacy endpoint as explanatory factors. The MMRM model will also include visit, treatment group by visit interaction, prior biologic use by visit, screening Hurley stage by visit, and baseline value by visit interaction as additional explanatory factors. In addition, treatment differences and their associated 95% confidence intervals will be presented.

For the MMRM model, an unstructured covariance matrix for repeated measure within a participant will be used. In case that convergence cannot be achieved, autoregressive (1) covariance structure will be used.

Descriptive statistics, such as mean, median, standard deviation, minimum and maximum, interquartile range for continuous variables, and counts and percentages for categorical variables will be used to summarize the data. Graphical data displays and subject listings may also be used to summarize the data.

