# 5.2. Analysis Specifications

## 5.2.1. Level of Significance

Unless otherwise specified, all statistical testing procedures will be performed at a 2-sided significance level of 0.05. Multiplicity adjustment was planned for the primary endpoint as specified in protocol Section 10.5.3 to maintain an overall Type I error of 0.05 or less for the primary endpoint analysis. Nominal p-values will be reported for other secondary analyses.

However, since this is a Phase 2 trial and stricter multiplicity adjustment for the primary endpoint at an overall alpha level of 0.05 is not required; a less stringent type I error controlled will be implemented instead. The study would be considered as positive if any of the comparisons for primary endpoint analysis (weekly injection group vs placebo, and every other week injection group vs placebo) is less than or equal to 0.05. Therefore, an overall Type I error rate will be maintained at 0.1 or less for the primary endpoint analysis. Nominal p-values will be reported for secondary analyses.

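### The AN count 0/1 and 0/1/2 comparisons leave out baseline AN count, which is strongly prognostic for a fixed threshold. The planned CMH test is valid but loses some precision.

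*SAP*

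**What the plan says.** SAP 5.4.3.2.2, under AN Count, compares "The proportion of participants achieving AN count of 0/1 and 0/1/2 respectively at Week 12 and Week 16" between each bermekimab group and placebo, without naming a test. The rule for binary endpoints in SAP 5.4.1.1 therefore governs: a CMH "test stratified by the prior biologic use (yes/no) and screening Hurley stage (II/III) with missing data imputed with Non-Responder Imputation (NRI").

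For continuous endpoints, including change in AN count, SAP 5.1 puts the "baseline value for the corresponding efficacy endpoint as explanatory factors" in the MMRM, together with a baseline-by-visit term. Baseline AN count also defines pre-specified HiSCR subgroups (SAP 2.5 and 5.3.6, repeated at Week 16 under 5.4.3.1.2), by category (3 to 5, 6 to 10, 11 or more) and by median split.

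Protocol 4.1 sets the entry minimum: "A total body count of abscesses and inflammatory nodules (A+N) of at least 3". No maximum is given.

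SAP 4.1 adds a general clause: "If imbalances are found at baseline, then additional analyses may be performed adjusting for baseline differences".

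On testing, SAP 5.2.1 states that "all statistical testing procedures will be performed at a 2-sided significance level of 0.05" and that "Nominal p-values will be reported for secondary analyses".

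**The concern.** HiSCR is relative to the patient's own baseline. AN 0/1 and AN 0/1/2 are not: they ask whether the count has fallen to a fixed number. A patient who enters with 3 lesions reaches 2 by losing one, while a patient who enters with 20 must lose 18. The SAP adjusts for baseline when the AN count is analysed as a change score, but not when the same count is cut at a fixed value. Screening Hurley stage is only a partial stand-in for lesion number.

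What is at stake is precision. With about 50 patients per arm, an omitted strong covariate widens the interval around the risk difference and lowers power. Lesion-count data are among those selected for the Week 16 lock, which SAP 2.4 says will mainly inform later development in HS, so tighter estimates would be useful there.

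**Working it through.** **1. The plan's own figure.** The only powered comparison is HiSCR at Week 12 (SAP 1.4): 60% vs 30%, two-sided 0.05, about 80% power.

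n = [z₀.₉₇₅·√(2·p̄·(1−p̄)) + z₀.₈₀·√(p₁(1−p₁) + p₂(1−p₂))]² / (p₁−p₂)², with p̄ = 0.45

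= [1.960·√0.495 + 0.842·√0.45]² / 0.09 = 41.97, so 42 per arm.

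This reproduces the plan. At the roughly 50 per arm actually randomized (150/3), power for HiSCR is 0.866. The documents state no power for AN 0/1 or AN 0/1/2.

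**2. How far each patient has to fall.** Required reduction = 1 − threshold/baseline.

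| Baseline AN | To reach ≤1 | To reach ≤2 |
|---|---|---|
| 3 | 67% | 33% |
| 10 | 90% | 80% |
| 20 | 95% | 90% |

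**3. How prognostic that makes baseline.** One mid-range scenario assumes: baseline log-normal with median 9 and log-SD 0.8, floored at 3; Week 12 count Poisson with mean equal to baseline × ratio (0.30 active, 0.60 placebo) × a log-normal patient effect with SD 0.5; and 12% dropout counted as non-response. Averaged over the two arms, the AN 0/1 rate is then about 44%, 20% and 5% in the SAP's own categories 3 to 5, 6 to 10, and 11 or more.

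**4. What adjustment gains.** Each simulation set has 50 per arm and compares the SAP's four-stratum CMH test with a logistic model containing the two stratification factors and log baseline AN count. Everything about the AN distribution, effect size, patient variability and dropout is assumed, because the documents do not give it.

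| Set | Main assumptions | Power gain (points) | Fall in variance of risk difference |
|---|---|---|---|
| A: 6 comparisons, Wald test | Ratios 0.33 vs 0.72, patient SD 0.9, baseline median 6 to 9, no dropout listed | 5.5 to 10.8 | 11 to 20% |
| B: 96 scenarios, score test | Baseline median 6 to 11, patient SD 0.5 to 1.3, ratios 0.25 or 0.30 vs 0.60, 12% dropout | 2.1 to 14.1, median 5.6 | not computed |
| B, both tests calibrated to 5% size | as above | 0.1 to 11.7, median 3.8 | not computed |
| C: 24 scenarios, Wald test | Baseline median 6 to 9, patient SD 0.5 or 0.9, with or without 12% dropout | 3.7 to 12.1, median about 6.5 | 9 to 24% |
| D: 18 scenarios, Wald test | 12% dropout | about 1.5 to 11, median about 5 | 5 to 23% |

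In set A, the gains for AN 0/1/2 are 76.6 − 70.0 = 6.6, 71.6 − 62.2 = 9.4 and 69.8 − 59.0 = 10.8. For AN 0/1 they are 66.9 − 61.0 = 5.9, 59.5 − 54.0 = 5.5 and 60.4 − 53.6 = 6.8.

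For AN 0/1/2 in the step 3 scenario (latent correlation of Hurley stage with baseline 0.5), power rises from 0.61 to 0.74, or by 12 points after size calibration. With a narrow baseline (median 6) and patient SD 0.9, the gain is 4 to 5 points, or 2 to 4 after calibration.

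**5. Type I error.** The CMH test holds at about 4 to 6% in set B. The score test in set B runs at about 5 to 7%, which is why the calibrated row matters. The Wald test stays close to the CMH test: 3.5 to 5.6% against 4.0 to 5.8% in set C, and about 4 to 7% for each in set D.

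**6. Extra CMH strata instead.** Adding the SAP's three AN categories gives 4 × 3 = 12 strata, about 100/12 ≈ 8 patients each in a pairwise comparison. In set B this changed power by −2.4 to +6.7 points, with a median of about zero.

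**The case against.** The strongest reply is that little depends on these tests. AN 0/1 and AN 0/1/2 are not in the endpoint list of Protocol 3.1; they fall under the additional responder analyses that Protocol 10.5.3.2 allows. Their p-values are nominal and the trial was not sized for them. One CMH test for all binary endpoints, matching the randomization factors, is conventional and valid. The AN data also get a baseline-adjusted MMRM with two supplementary analyses. All of this stands, and it limits the point to a cheap improvement.

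Four stronger readings are tempting, and the documents do not support them.

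- A reader might infer a fixed loss of 5 to 11 points. That range comes from set A alone, with one effect size, one patient SD and no dropout. After size calibration in set B, 71% of scenarios fall below 5 points.
- A reader might infer bias, or that a baseline imbalance passes in full into the result. Randomization protects the CMH test, its error rate holds, and stratifying by Hurley stage absorbs part of any imbalance to the extent that it tracks lesion count.
- A reader might take the SAP 4.1 clause to leave the main analysis open after unblinding. It only permits additional analyses; the CMH test stays.
- A reader might extend the point to complete elimination of abscesses, draining fistulas or inflammatory nodules. Those comparisons are restricted to patients who have the lesion at baseline, the subset sizes are unknown, and no calculation here covers them.

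**Conclusion.** The point holds as a matter of efficiency. The planned test for AN 0/1 and AN 0/1/2 omits a covariate that is already collected, already used elsewhere in the SAP, and strongly prognostic because the threshold is absolute.

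Across plausible scenarios at 50 per arm, the loss is roughly 0 to 14 power points, typically about 4 to 6. Equivalently, adjustment would lower the variance of the risk difference by about 5 to 24%. The gain is largest with a wide baseline spread and modest between-patient variability, and nearly vanishes with a narrow baseline and large variability. These figures rest on the assumed inputs in the working and should be quoted only with them.

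Nothing here touches the primary test. In simulated data of the same kind, the within-arm correlation between log baseline AN count and a 50% reduction was below 0.05, against 0.30 to 0.47 for the fixed thresholds.

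**What to change.** In SAP 5.4.3.2.2, pre-specify for AN 0/1 and AN 0/1/2 at Weeks 12 and 16:

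- a logistic model with treatment, prior biologic use, screening Hurley stage and continuous log baseline AN count, under the existing non-responder rule;
- the p-value from the model's treatment term (Wald);
- the standardized (marginal) risk difference with 95% CI as the reported effect;
- the stratified CMH test as a sensitivity analysis;
- a named fallback, either a Firth penalty or the CMH test, with the condition that triggers it if responses are sparse.

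Do not implement this as extra CMH strata. A sentence noting that baseline AN count is already used in the MMRM and the HiSCR subgroups would keep the SAP coherent.

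The cost is a few lines of text and a standard model, with no new data. There are two small downsides. The fallback must be specified. The p-value also tests a conditional odds ratio while the interval is for a marginal risk difference, so the two can disagree in borderline cases; the SAP should say which one is read as the test.

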# 5.2.2. Data Handling Rules

No imputation will be performed for missing baseline values.

For the main analysis of primary endpoint of HiSCR at Week 12, participants who discontinued treatment will be considered as a non-responder from that point onward. The remaining missing data will be imputed as non-responder. Supplementary analyses will be performed and include (1) using observed data regardless of whether the participant discontinued treatment or have missing data, and (2) data after treatment discontinuation will be considered as missing, missing response will be imputed by multiple imputation methods under the assumption of missing at random. Similar data handling rules (i.e., main analysis with non-responder imputation and

2 supplementary analyses) will also be applied for HiSCR response over time through Week 16. The following data handling rules will be applied for other endpoints:

Binary secondary endpoints:

• Analyses will be similar to the main analysis of the primary endpoint. A participant who discontinued treatment will be considered as a non-responder from that point onward. The remaining missing data will be imputed as non-responder.

Continuous secondary endpoints:

- If a participant discontinued treatment, zero will be assigned to improvement or percent improvement. Remaining missing data will not be imputed. A MMRM model will adjust for missing post baseline data and all available data from the 3 treatment groups through Week 16 or from Week 16 through Week 36 will be included. Under the assumption of missing at random (MAR), the missing data will be accounted for through correlation of repeated measures in the model.
- In addition, supplementary analyses will be performed for the analyses related to (a) change from baseline in AN count (Section 5.4.3.2.2) and (b) change from baseline in HSSD past 24 hours pain (Section 5.4.3.5.3.2) endpoints using
  - Observed data regardless of whether the subject discontinued treatment or have missing data.
    - Data after treatment discontinuation will be considered as missing, missing data will be addressed by MMRM model.

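### The generic non-responder rule also covers flare, an unfavourable cumulative event, so under the usual coding dropouts with no recorded flare count as flare-free

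*SAP*

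**What the plan says.** SAP 5.4.3.2.2, under AN Count, includes a between-group comparison at Weeks 12 and 16 of "The proportion of participants who experienced at least one flare", and a descriptive summary of the same measure at Week 36. A flare is "at least a 25% increase in AN count with a minimum increase of 2 AN count relative to baseline". It is therefore a bad outcome, and a cumulative one: one qualifying count is enough.

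The missing-data rule for binary secondary endpoints is in SAP 5.2.2: "A participant who discontinued treatment will be considered as a non-responder from that point onward", followed by "The remaining missing data will be imputed as non-responder". SAP 5.4.2 extends it: "Unless otherwise specified, data handling rules specified in Section 5.2.2 will be applied to these secondary analyses". For over-time summaries it adds: "For binary endpoints, participants with missing response status will be considered non-responders for the over time analyses". SAP 5.4.1.1 specifies the stratified CMH test for binary response endpoints, "with missing data imputed with Non-Responder Imputation (NRI) defined in Section 5.2.2".

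No exception for flare appears in these sections or beside the flare analysis. The observed-data and missing-at-random supplements are planned for HiSCR, change in AN count and HSSD 24-hour pain, but not for flare.

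**The concern.** For HiSCR and the other endpoints that a patient achieves, setting a dropout to non-responder counts the dropout as a failure. The same code applied to flare says that the event did not happen. A participant who stops treatment with no flare yet on record is then credited with the good outcome.

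That runs against the SAP's own principle. SAP 5.3.2 makes discontinuation a non-response by a composite strategy, and SAP 5.2.2 assigns zero improvement for continuous endpoints. Discontinuation may also be linked to worsening. Protocol 5.3 requires treatment to stop when the investigator judges that disease progression makes continuing contrary to the patient's interest, and Protocol 2.11.3 requires it when more than two lesion interventions are needed.

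The early termination visit adds a further difficulty. Lesions are counted there (Protocol 5.1 and 5.2.2), but that visit may follow discontinuation. A flare first seen at it may be overwritten, because the rule acts from discontinuation onward.

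At stake are the size, and possibly the direction, of the flare comparison whenever the arms differ in how many participants leave without a recorded flare.

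**Working it through.** **The plan's own figures.** The SAP states no flare rate, flare difference or dropout rate. Its only sample-size figure is for HiSCR. For 60% versus 30%, two-sided 0.05 and 80% power, the pooled-variance chi-square formula gives 42 per arm (126 in total) with power 80.0%. That reproduces SAP 1.4 and is not affected here. Enrolling 150 rather than 126 leaves room for dropout of 1 − 126/150 = 16%.

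**Inputs, all assumed for flare.** f is the flare rate among completers, d the share who discontinue or are missing, and q the share of those with a flare already recorded. For simplicity q is the same in both arms. The benchmark assumes that dropouts, if followed, would have flared at rate f.

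**Formulas.**
- Non-responder = criterion not met: reported rate = (1 − d)f + dq. The shortfall against f is d(f − q), which for q from 0 to f is largest at q = 0 and zero at q = f.
- Non-responder = flare: reported rate = (1 − d)f + d, whatever q is.

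**Main example: f = 30% in both arms, d = 20% placebo and 10% active.**
- Criterion not met, q = 0: 0.80 × 0.30 = 24% versus 0.90 × 0.30 = 27%. Placebo looks better by 3 points.
- Criterion not met, q = 30%: 0.24 + 0.20 × 0.30 = 30% versus 0.27 + 0.10 × 0.30 = 30%. No bias.
- Flare coding: 0.24 + 0.20 = 44% versus 0.27 + 0.10 = 37%. Active looks better by 7 points.

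**Range: f = 40% in both arms.** Rates are placebo versus active.

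| d placebo / active | q | Criterion not met | Flare |
|---|---|---|---|
| 16% / 16% | 0 | 33.6% vs 33.6% | 49.6% vs 49.6% |
| 10% / 20% | 0 | 36% vs 32% | 46% vs 52% |
| 10% / 20% | 30% | 39% vs 38% | 46% vs 52% |
| 10% / 20% | 40% | 40% vs 40% | 46% vs 52% |
| 5% / 30% | 0 | 38% vs 28% | 43% vs 58% |
| 5% / 30% | 30% | 39.5% vs 37% | 43% vs 58% |

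**Effect on the nominal test.** This was simulated with 50 per arm, an unstratified two-sided chi-square test, f = 40% in both arms and q = 0. Under criterion-not-met coding, the chance of p ≤ 0.05 favouring active is 2.5% at 16%/16% dropout, 6.1% at 10%/20% and 18.2% at 5%/30%. Under flare coding, the chance of p ≤ 0.05 favouring placebo is 9.5% at 10%/20% and 34.4% at 5%/30%.

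Where dropout is unequal, the two codings can therefore point in opposite directions from the same data.

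**The case against.** Four objections have weight.

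- **Recorded flares survive.** A reader might infer that anyone who stops after worsening becomes flare-free. The documents do not support that. The endpoint asks for at least one flare, and the rule acts only from discontinuation onward. Protocol 5.2.1 schedules lesion counts at Weeks 1, 3, 5, 7, 9, 12 and 16, so a flare seen at any of these while on treatment stays on record. Patients who worsen before stopping are the likeliest to have one, which moves q up and the bias down.
- **The SAP does not define the coding.** It never says that a non-responder for flare is flare-free, and SAP 5.4.1.1 speaks of response endpoints. A programmer could code the bad outcome, or leave flare outside the rule. This stands, but it leaves the direction open rather than removing the problem.
- **Worst-case coding has its own bias.** In the main example it errs by 7 points where criterion-not-met coding errs by 3. With completer rates of 30% placebo and 20% active and the same 20%/10% dropout, criterion-not-met coding at q = 0 gives 24% versus 18% (6 points), and flare coding gives 0.24 + 0.20 = 44% versus 0.18 + 0.10 = 28% (16 points), against 10 points among completers. This also stands, and is why an observed-data analysis is needed beside it.
- **The endpoint is minor.** Flare is not among the endpoints in Protocol 3.1, and its p-values are nominal.

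**Conclusion.** The point holds as a specification gap worth closing. As written, the generic rule reaches an unfavourable event. Under the usual coding it removes potential flares from participants who leave without one on record, which favours the arm with more of them. In the assumed scenarios with unequal dropout, the false difference at q = 0 ranges from 3 to 10 points, and it vanishes when q = f. Flare rates, dropout rates, q and the benchmark for dropouts are all assumptions.

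Three stronger readings are tempting but not supported. The bias does not systematically favour bermekimab, since its direction depends on which arm loses more participants without a recorded flare. Flare is not the only binary endpoint worded in the unfavourable direction: SAP 5.4.3.5.5.2 counts a reduction of half an SD in EQ VAS, although SAP 5.4.3.5.5.1 puts best health at 100, so that wording needs the same check. And the primary HiSCR analysis, its multiplicity rule and the sample size are untouched. The practical consequence is confined to a secondary lesion-count result, though SAP 2.4 lists lesion counts among the Week 16 data to be used in planning further development.

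**What to change.** In SAP 5.2.2 and 5.4.3.2.2, exempt flare from the generic binary rule and state that:

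1. every recorded flare counts, including one first seen at the early termination visit;
2. treatment discontinuation before the analysis week with no recorded flare counts as a flare, in line with the composite strategy used for HiSCR;
3. an isolated missed visit does not count as a flare, which matters because the COVID-19 appendix expects missed visits;
4. an observed-data analysis of flare is given as a supplement.

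Settle this before any sponsor staff are unblinded at the Week 16 lock (SAP 1.5.2), so that the coding cannot be chosen with results in view.

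The cost is a few sentences and one extra table. Reported flare rates will look less favourable, and the composite coding can overstate a difference when dropout is unequal. The observed-data version lets the reader see how much of any difference comes from dropout.
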